The goals of this study are: 1) to improve our understanding of the thermoregulatory mechanisms of individuals with tetraplegia when exposed to cold, 2) to determine if cognitive performance is affected after a decrement in Tcore, and 3) to determine if administration of an alpha-adrenergic agonist (midodrine) delays or decreases the expected downward drift in Tcore and possible deterioration of cognitive performance.

In order to address our goals, we have designed a study methodology which consists of comparing the physiological and subjective responses of the two study groups (tetraplegia versus AB controls) from thermoneutral (27°C) to cool (18°C) environments in the seated position. On a 2nd visit, the subjects with tetraplegia who completed the first visit, will be given midodrine while seated prior to being placed in the cool environment to compare their responses with midodrine to their responses to the identical challenge without midodrine.

Overall Objective: The overall objective is to identify and address the physiological and cognitive problems that persons with spinal cord injury (SCI) face when exposed to routinely encountered cool temperatures.

- Specific Aims: during exposure to a cool environment (18°C) for up to 120 min in the seated position:

Primary Specific Aim: To determine the change in: (1) Tcore and to assess (2) cognitive performance (attention, processing speed, working memory, and executive function) before and

after exposure to cool temperatures. **Primary Hypotheses:** Based on our pilot data: (1) Sixty-six percent of persons with tetraplegia and none of the controls will demonstrate a decline of 1.0°C in Tcore; (2) Eighty percent of persons with tetraplegia and 30% of controls will have a decline of at least one T-score in Stroop Interference scores (a measure of executive function).

Secondary Specific Aims: To determine the change in: (1) the average of distal skin temperatures, (2) metabolic rate, and (3) subjective rating of thermal sensitivity. **Secondary Hypotheses:** Persons with tetraplegia will have less of a percent change in average distal skin temperatures and metabolic rate, and report blunted thermal sensitivity ratings compared with able-bodied (AB) controls.

Tertiary Specific Aim: To determine if a 10 mg dose of midodrine will (1) reduce the decrease in Tcore and (2) prevent or delay the decline in cognitive performance in the group with tetraplegia.

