Tertiary Hypothesis: Because the one-time, off-label use of midodrine will address the primary systemic impairment to cold exposure in persons with tetraplegia, lack of peripheral vasoconstriction, the induced vasoconstriction will serve to reduce cutaneous heat losses and will be anticipated to blunt the decrease in Tcore and delay the decline in cognitive performance compared to cool exposure without drug administration.

METHODS

Research Design and Methods: A prospective, two-group comparative study will be performed to determine the effects of cold thermal challenge on Tcore, cognitive performance, distal skin temperatures (Tsk), metabolic rate (VO₂), and thermal sensitivity (TS) in the seated position in individuals with tetraplegia and in a matched AB control group (Visit 1). During Visit 2, a prospective, within-group comparative study will be performed to determine the effects of cold thermal challenge on Tcore, cognitive performance, Tsk, VO₂, and TS only in individuals with tetraplegia after midodrine administration compared to their response on Visit 1.

A prospective, two-group comparative study will be performed to determine the effects of cold thermal challenges on core temperature measured by rectal thermocouple (Tre), skin temperature by surface thermocouples (Tsk), cognitive performance by [digit span section of the Wechsler Adult Intelligence Scale-Fourth Edition (WAIS-IV), Stroop Color and Word tests, Symbol Digit Modalities Test (SDMT), memory and delayed recall sections of the Montreal Cognitive Assessment (MoCA)], metabolic rate measured by oxygen consumption (VO₂), and thermal sensation by the thermosensitivity cold scale in the seated position in individuals with tetraplegia and in a matched AB control group (Visit 1). During Visit 2 a prospective, within-group comparative study will be performed to determine the effects of thermal challenge on Tcore, skin temperature, cognitive performance, metabolic rate, and thermal sensation in individuals with tetraplegia who have participated in Visit 1 and in those same individuals who repeat the Visit 1 challenge identically, except for the administration of midodrine prior to the cold challenge while in the seated position (Visit 2).

Subjects: Fifteen subjects with tetraplegia (C4-T1) and 15 non-SCI control subjects matched for age (\pm 5 years), and gender will be recruited for study.

Subject Recruitment:

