Statistical Analyses: *Visit 1:* Depending on the data distribution, parametric or non-parametric analyses will be performed. For the within-group comparisons, paired-t and Wilcoxon signed rank tests will be conducted to determine intra-group differences in the dependent variables. For the between-group comparisons, unpaired-t and Mann-Whitney U tests will be performed to determine between-group differences in the percentage change (from thermoneutral to cool) of the dependent variables (Tcore, cognitive performance, Tsk, and VO₂).

Visit 2 (with midodrine): Depending on the data distribution, parametric or non-parametric analyses will be performed. Within the group with tetraplegia, paired-t or Wilcoxon signed rank tests will be used to determine differences in the percentage change (from thermoneutral to cool) of the dependent variables (Tcore, cognitive performance, Tsk, VO₂), without midodrine (Visit 1) compared to with midodrine (Visit 2).

Sample size: The primary outcome variables are Tcore and cognitive performance. For Tcore, using our preliminary data obtained post cold exposure in tetraplegic and AB subjects, mean Tcores of $35.95 \pm 0.63^\circ\text{C}$ and $37.3 \pm 0.28^\circ\text{C}$ were demonstrated, respectively. The difference between the groups for these values yields a power of 99.9% at an alpha of 0.05 with 8 subjects

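### Tcore and Stroop Interference are compared as percentage change although neither scale has a true zero; absolute change in the hypotheses' own units is a small, cheap improvement

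*Combined protocol and SAP*

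**What the plan says.** In the combined protocol and SAP, the Visit 1 paragraph of Statistical Analyses uses unpaired t or Mann-Whitney tests for "between-group differences in the percentage change (from thermoneutral to cool) of the dependent variables (Tcore, cognitive performance, Tsk" and VO₂. The Visit 2 paragraph states that "paired-t or Wilcoxon signed rank tests will be used to determine differences in the percentage change" in the same variables, without and with midodrine. No reason for percentages is given and no baseline adjustment is named. The within-group sentence for Visit 1 ("paired-t and Wilcoxon signed rank tests will be conducted to determine intra-group differences in the dependent variables") has no percentage wording, so the point does not reach it.

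The Sample size section names Tcore and cognitive performance as the primary outcome variables. Both primary hypotheses under Specific Aims are in absolute units. Stated proportions of each group "will demonstrate a decline of 1.0°C in Tcore" or "will have a decline of at least one T-score in Stroop Interference scores". Only the secondary hypothesis is in percent: persons with tetraplegia "will have less of a percent change in average distal skin temperatures and metabolic rate".

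The comparison groups are 15 subjects with tetraplegia and "15 non-SCI control subjects matched for age" and gender. Baseline cognition is not a matching factor.

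Statistical Analyses says only cognitive performance. The battery in Research Design and Methods includes digit span, "Stroop Color and Word tests, Symbol Digit Modalities Test (SDMT), memory and delayed recall sections of the Montreal Cognitive Assessment (MoCA"). Stroop Interference in T-scores is the one cognitive measure given a hypothesis and a power figure, so its use as a T-score in the percentage analysis is an inference. For the other tests the documents do not say whether raw or standard scores are analysed.

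**The concern.** A percentage of baseline has a fixed meaning only when zero means none of the quantity. That holds for VO₂ but not for °C or a T-score. On those two scales the same physical or cognitive change gives a different percentage on an equivalent scale with another origin, and equal losses from unequal baselines give unequal percentages.

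At Visit 1 the groups are not randomised and could differ on Stroop before cooling. If the tetraplegia group starts lower, percentage change enlarges its apparent decline; if it starts higher, percentage change shrinks it. The reported result would also not be in the units of either primary hypothesis. At Visit 2 the same people are compared with themselves, so only the scale-and-units argument applies.

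**Working it through.** **The plan's own figures.** For Stroop responders, 83% v 33% with 15 per group and a pooled proportion of 0.58:

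- Null SE = √(2×0.58×0.42/15) = 0.1802, and 1.96×0.1802 = 0.3532.
- Alternative SE = √((0.83×0.17 + 0.33×0.67)/15) = 0.1554.
- z = (0.50 − 0.3532)/0.1554 = 0.945, so power is 82.75%, as stated.

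The same method gives 99.59% for 66% v 0%. The 99.9% for Tcore means also reproduces (99.92% by noncentral t, 8 per group, difference 1.35, SD 0.487). None of the three uses percentage change, so none is altered here.

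**Scale dependence.**

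- A 1.0°C fall ending at the pilot mean of 35.95°C starts at 36.95°C: 1.0/36.95 = 2.71%. In Fahrenheit it is 1.8/98.51 = 1.83%.
- Take the T-score as mean 50, SD 10 (assumed convention). A 5-point loss is 5/40 = 12.5% from 40 and 5/50 = 10.0% from 50.
- On a mean-100, SD-15 metric, S = 100 + 1.5(T − 50), the same losses are 7.5/85 = 8.8% and 7.5/100 = 7.5%.
- Equal 10% losses on the T-score (4 from 40, 5 from 50) become 6/85 = 7.1% and 7.5/100 = 7.5%. Equal proportional loss is therefore not a stable null hypothesis. Absolute change gives the same p-value on all these linear scales.

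**Stroop at Visit 1, calibrated to the plan's responder rates.** Assumptions: normal changes; change SD 2 to 6; baseline SD 8; change independent of baseline; 15 per group; two-sided t test at 0.05; 40,000 simulated trials per cell. The documents give no Stroop baselines or SDs.

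If a proportion p declines by at least 1 point, the mean change is −1 − SD×Φ⁻¹(p). With SD 4, 80% v 30% gives −4.37 v +1.10. The standardised difference is 0.842 + 0.524 = 1.37 (1.39 for 83% v 33%) whatever the SD.

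| Mean baseline, tetraplegia v control | Power, absolute | Power, percentage |
|---|---|---|
| Equal | 95–96% | 94–95% |
| 40 v 50 | 95–96% | 96–98% |
| 50 v 40 | 95–96% | 87–91% |

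Giving both groups the control change (baselines 45 v 50, 40 v 50, 50 v 40), false positives are 4.8–5.6% for percentage change and 4.8–5.3% for absolute change.

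**Stroop if both groups truly lose several points.** With an equal 4-point loss, change SD 4 and baseline SD 8, percentage change rejects in about 9% of trials at 40 v 50 and just under 6% at 45 v 50. Absolute change stays near 5%. With an equal 5-point loss, change SD 2 and 40 v 50, percentage change rejects in 27%.

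**Tcore.** With an assumed baseline of 37 ± 0.35°C, percentage and absolute change correlate above 0.999. Power is 82.0% for both, and the verdict differs in about 0.2% of trials.

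**Visit 2, Stroop.** Paired false positives for percentage change are 4.8–5.1% when mean baseline is the same at both visits. They reach 5.0–8.5% only if it shifts by 4 points.

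**Skin temperature.** With an equal 4°C fall, baseline SD 1 and change SD 0.6 or 1.0 (all assumed), percentage change rejects in 10–20% of trials at 30 v 32°C and 6.2–8.6% at 31 v 32°C. Absolute change rejects in about 5%.

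**The case against.** The strongest reply concerns consequence. Every scenario with clearly inflated Stroop error needs controls to lose 4 to 5 T-points as well. Under normal changes that makes Φ((loss − 1)/SD) of controls decliners by at least one point: 69% (loss 4, SD 6), 77% (loss 4, SD 4), 84% (loss 5, SD 4) and 98% (loss 5, SD 2). The pilot saw 2 of 6 and the plan hypothesises 30%. A reader might infer from the 9% or 27% figures that the Visit 1 test has a materially inflated type I error. The documents do not support that. Six controls cannot exclude such losses, but they make them unlikely. This part of the objection stands.

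It also stands that Tcore results barely move, that no error is shown at Visit 2 unless mean baseline shifts, and that percentage change has slightly more power when the tetraplegia group starts lower. The documents use °C and T-scores throughout, so an analyst switching to another scale is a way of showing the defect, not a forecast.

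What remains is that the metric has no fixed meaning on these scales, does not match the hypotheses, and makes Stroop power depend on an unmatched baseline. A preference for proportional loss does not rescue it, because equal proportions on one standard-score scale are unequal on another.

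**Conclusion.** The point holds as a minor one about units and robustness. For Tcore, absolute change improves consistency with the 1.0°C hypothesis and practically nothing else. For Stroop at Visit 1, it keeps power at 95–96% whatever the baseline gap, while percentage change ranges from 87% to 98% across gaps of 10 points in either direction. A 10-point gap is large, a full SD on the usual T-score convention. False positives are near 5% with both metrics at the plan's responder rates.

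These figures rest on assumed normal changes, baseline SD 8, change SD 2 to 6 and the inference that Stroop is analysed as a T-score. A reader might also infer that the stated powers or the sample size are undermined, or that the midodrine comparison is biased. Neither follows: no stated power used percentage change, and at Visit 2 the argument is scale and units only.

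**What to change.** In both paragraphs of Statistical Analyses, for the between-group and between-visit comparisons:

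- analyse Tcore as absolute change in °C and Stroop Interference as absolute change in T-score points, with the same t, Mann-Whitney or Wilcoxon tests;
- do the same for any other cognitive test scored as a standard score, and state which score each test uses;
- keep percentage change for VO₂;
- for skin temperature, which shares the no-true-zero flaw, test absolute °C change beside the percentage change that the secondary hypothesis states.

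Fix the choice before outcome data are examined.

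The cost is the rewording of two paragraphs and one additional skin-temperature analysis. Data, sample size and stated powers are unchanged. The small downside is that, if the tetraplegia group starts lower on Stroop, absolute change gives up 1 to 2 points of power that percentage change draws from the baseline gap. The change does not supply a test of the hypothesised responder proportions (66% v 0%; 80% v 30%), which is a separate issue.

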per group (double-sided). Four of the 6 subjects with tetraplegia (66%) had a decrease of $\geq 1.0^{\circ}\text{C}$ while no control demonstrated a decline $> 0.297^{\circ}\text{C}$ in Tcore (0%). Cognitive performance will be assessed after a Tcore decline of 1.0°C in subjects with tetraplegia. Using 66% (tetraplegia) versus 0% (control) with a count of 15 per group, the power is 99.59% at an alpha of 0.05. We are hypothesizing that 66% of subjects in the SCI group will have a decline of 1.0°C in Tcore while none of the controls will demonstrate the same decline. We are well-powered to test this endpoint. For cognitive performance, preliminary data indicated that 5 of 6 subjects with tetraplegia (83%), compared to 2 of 6 AB subjects (33%), demonstrated a decline of ≥ 1 T-score in Stroop Interference scores post cold exposure. Using 83% (tetraplegia) versus 33% (control) with a count of 15 per group, the power is 82.75% at an alpha of 0.05 (double-sided).⁷⁶ We hypothesize that 80% of subjects in the SCI group will have a decline of at least 1 T-score in Stroop Interference scores while 30% of controls will demonstrate that same decline. We are well-powered to test this outcome.

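### Tcore and cognitive performance are both primary at alpha 0.05 with no rule controlling error across them, and the analysis section does not name the primary cognitive score

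*Combined protocol and SAP*

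**What the plan says.** The sample size section of the combined protocol and SAP names two primaries: "The primary outcome variables are Tcore and cognitive performance".

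Each has its own power calculation.
- **Tcore, means:** the stated difference "yields a power of 99.9% at an alpha of 0.05 with 8 subjects" per group, two-sided.
- **Tcore, responders** (a decline of 1.0°C): "Using 66% (tetraplegia) versus 0% (control) with a count of 15 per group", "the power is 99.59% at an alpha of 0.05".
- **Cognition, responders** (a decline of at least one T-score in Stroop Interference): "Using 83% (tetraplegia) versus 33% (control) with a count of 15 per group", "the power is 82.75% at an alpha of 0.05 (double-sided").

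The definition of the cognitive primary varies by section.
- The Primary Specific Aim speaks of "cognitive performance (attention, processing speed, working memory, and executive function"), which is four domains.
- The Primary Hypotheses name one cognitive measure, Stroop Interference, and expect a decline in 80% of the tetraplegia group against 30% of controls.
- Research Design and Methods lists four instruments: WAIS-IV digit span, the Stroop tests, the SDMT, and the "memory and delayed recall sections of the Montreal Cognitive Assessment (MoCA").
- Statistical Analyses, for the Visit 1 between-group comparison, plans unpaired t or Mann-Whitney tests on percentage change. It lists cognitive performance as a single dependent variable and names no score or composite.

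No section gives an alpha split, a test order, a gate between the primaries or a rule that both must succeed.

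**The concern.** Two separately claimable primaries at 0.05 each have a joint false-positive rate above the 5% on which the power figures rest. The second primary is also not tied to one score where the tests are specified. An analyst following only the Statistical Analyses section could test digit span, Stroop, SDMT and MoCA, and present whichever was significant as the cognitive result. In a study of 15 per group, a chance difference on one test could then be reported as a primary finding.

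**Working it through.** **1. Reproduce the plan's power figures.** Pooled two-sided formula with n = 15 per group and p̄ the mean of the two rates:

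power = Φ{ [ |p1 − p2| − z·√(2p̄(1−p̄)/n) ] / √( [p1(1−p1) + p2(1−p2)]/n ) }, with z = 1.960 at alpha 0.05.

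- Stroop, 0.83 vs 0.33: (0.500 − 1.960 × 0.1802)/0.1554 = 0.944, so power is 82.75%, as stated.
- Tcore, 0.66 vs 0: (0.660 − 1.960 × 0.1717)/0.1223 = 2.645, so power is 99.59%, as stated. That sentence does not give the sidedness; two-sided reproduces it.
- Tcore means, 35.95 (SD 0.63) vs 37.3 (SD 0.28), 8 per group: pooled SD = √((0.63² + 0.28²)/2) = 0.487. The noncentral t gives 99.92%, against 99.9% stated.

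So the responder power figures belong to a two-sided 0.05 test of each primary on its own.

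**2. Chance of at least one false primary claim, all nulls true.** With k independent tests at 0.05 it is 1 − 0.95^k.

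| Tests that can support a primary claim | k | Rate |
|---|---|---|
| Tcore + Stroop Interference | 2 | 9.75% |
| Tcore + four cognitive instruments | 5 | 22.6% |

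**3. Allow for correlation** (assumed values, since the documents give none; simulated for more than two tests).
- Two primaries correlated 0.5: 9.1%.
- Five tests all equally correlated at 0.3, 0.5 and 0.7: 20.9%, 18.3% and 14.9%.
- Tcore independent, four cognitive tests correlated 0.5: 19.8%; correlated 0.9: 13.9%.

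**4. Suppose the Tcore effect is real,** as the pilot means suggest. Only a cognitive result can then be false.
- Stroop Interference alone: 5%.
- Four open, independent cognitive tests: 1 − 0.95⁴ = 18.5%. With correlation 0.5 it is 15.6%.

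**5. Power under possible remedies,** at the hypothesised 80% vs 30%.
- No adjustment: (0.500 − 1.960 × 0.1817)/0.1571 = 0.917, power 82.0%.
- Fixed order, Tcore then Stroop, assuming independent tests: 0.8203 × 0.9959 = 0.817. Whatever the dependence, it is at least 0.8203 − (1 − 0.9959) = 0.816.
- Bonferroni, 0.025 each (z = 2.241): (0.500 − 2.241 × 0.1817)/0.1571 = 0.591, power 72.3%.

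**The case against.** The strongest reply is that the plan already chooses its cognitive measure. The Primary Hypotheses name Stroop Interference, and the sample size section powers that score alone and repeats the hypothesis. On that reading the family is two tests and the rate about 10%. This stands, and it is the best-supported reading. It does not remove the gap: the primary aim spans four domains, the analysis section never limits the test to Stroop, and two uncontrolled primaries remain.

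Three further points also stand.
- The figures of 10% and 23% are worst-case rates that need Tcore to be null, which the pilot data make unlikely.
- Alpha 0.05 appears only in the power statements. Testing each primary at 0.05 is therefore a reasonable inference, not a stated rule.
- Whether to adjust across distinct hypotheses in a small physiological comparison is partly convention. If both primaries had to succeed, the rate would be at most 5%, but the plan does not say so.

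A reader might infer more than the documents support.
- One inference is that the plan lets any significant cognitive test count as a primary success. No section says this; the analysis section is only silent on the score.
- Another is a rate of about 26%. That needs six tests (1 − 0.95⁶ = 26.5%), reached for example by counting the MoCA memory and delayed recall sections as separate scores, a count the documents do not make.

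**Conclusion.** The concern holds in limited form. There are two primaries, each powered at 0.05, with no rule for error across them and no cognitive score fixed in the analysis section. With all nulls true and independent tests, the rate is about 10% on the best-supported reading. About 23% is an upper value that applies only if all four instruments may support the claim; assumed correlations of 0.3 to 0.7 among all five tests bring it to about 21% to 15%.

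The more realistic risk arises when the Tcore effect is real: 5% if Stroop Interference is the only cognitive primary, and up to about 18.5% if four tests are left open. Naming the score is therefore the main practical protection. At the planned rates a Tcore gate opens about 99.6% of the time, so it matters chiefly if Tcore shows no difference. This is a wording change that should be made; it does not show that the design is unsound.

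**What to change.** In the Visit 1 between-group analysis:

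1. Name Stroop Interference as the sole cognitive primary.
2. Test in fixed order, each at two-sided 0.05: Tcore first, then Stroop Interference only if Tcore is significant. This holds the error across the two primaries at 5%.
3. State one test form for each primary: either the responder proportion used in the hypotheses and power figures, or the percentage change used in Statistical Analyses.
4. Treat digit span, SDMT, the MoCA items and other Stroop scores as secondary, with nominal p-values.

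The cost is one paragraph of wording, with no added subjects or measurements. On the responder figures and assuming independent tests, Stroop power falls from 82.0% to about 81.7%, against 72.3% under Bonferroni. Stroop cannot be claimed as confirmatory if Tcore is not significant, a chance of about 0.4% at the planned rates (1 − 0.9959). If percentage change is chosen, these power figures do not carry over, because the documents give no Stroop mean or SD.
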